Study Protocol

- NCT Number: NCT07174544
- Organization's Unique Protocol ID: MC23FNSI0059
- Official Title: Mobile Self-Management Program Integrating Positive Psychology and Behavioral Activation for Stress Reduction in Young Adults: A Community-Based Randomized Controlled Trial
- Secondary IDs: Other Grant/Funding Number: NRF-2022R1A2C1011568
- Grantor or Funder Organization: National Research Foundation of Korea
- Document Date: 06/30/2025
- Brief Title: Mobile Self-Management Program for Stress Reduction in Young Adults
- Study Type: Interventional

1. Background and Rationale

In South Korea, young adults experience heightened stress stemming from academic and economic pressures, yet rates of treatment-seeking and service utilization remain low. Although mobile and online mental health programs have become increasingly available, few have been rigorously tested, particularly among non-clinical populations. This underscores the need to develop and validate evidence-based digital interventions. Stress during young adulthood is a critical mental health concern, closely linked with depression, anxiety, and diminished resilience. Mobile interventions offer accessible and scalable methods to support stress management and overall well-being. Both Positive Psychology (PP) and Behavioral Activation (BA) are empirically supported approaches that enhance psychological functioning and alleviate distress. The present study investigates the effectiveness of a mobile self-management program that combines PP and BA strategies to reduce stress and improve associated outcomes among young adults reporting elevated stress.

2. Objectives

This study sought to evaluate a mobile self-management program integrating Positive Psychology (PP) and Behavioral Activation (BA) as a mental health intervention for young adults in South Korea. The program was grounded in established theoretical frameworks and designed to (1) enhance positive emotional experiences, (2) help participants identify their personal strengths, (3) encourage engagement in strengths-based activities, and (4) support planning for a meaningful and fulfilling future. These goals drew on PP principles while incorporating BA techniques to promote and sustain positive affect and adaptive behaviors in young adults. Using a randomized controlled trial design, the study examined the program's effectiveness in improving psychological outcomes—including stress, depression, anxiety, and resilience—among young adults with elevated stress, as well as its usability and perceived quality.

Primary Objective:

- To evaluate whether a mobile self-management program integrating PP and BA reduces perceived stress in young adults with elevated stress.
- To assess whether the program improves depression, anxiety, and resilience.

Secondary Objectives:

- To evaluate usability and perceived quality of the mobile interventions.

3. Study Design

This study employed a randomized controlled trial with a wait-list control design to evaluate the effects of a mobile-based self-management program for young adults experiencing elevated stress in community settings in South Korea.

4. Study Setting

Participants were recruited nationwide in South Korea through both offline and online platforms. Recruitment sites included youth centers, mental health welfare centers, and a suicide prevention center. The intervention was delivered entirely via a mobile application, and outcome assessments were conducted online.

5. Eligibility Criteria

Inclusion Criteria:

- Age 19–34 years at the time of participation
- Proficiency in using digital devices
- Use of an Android-based smartphone or tablet
- Score ≥ 14 on the Perceived Stress Scale–10 (PSS-10)
- Provision of informed consent for random assignment

Exclusion Criteria:

- Score < 14 on the PSS-10
- Declines random assignment

6. Interventions

Experimental: Intervention Group

Participants assigned to the intervention group received a text message with a link to install the *DodaMe* mobile self-management program, which integrates Positive Psychology (PP) and Behavioral Activation (BA). The intervention lasted eight weeks, consisting of:

- **Guided Phase (Weeks 1–4):** Weekly objectives included (1) enhancing positive affect, (2) identifying personal strengths, (3) applying strengths in daily life, and (4) planning for a positive future. Program activities involved emotional check-ins, gratitude journaling, mindfulness practice, positive behavioral tasks, and goal setting.
- **Self-Directed Phase (Weeks 5–8):** Participants voluntarily selected from 10 recommended activities tailored to their strengths to encourage continued engagement and self-management.

Assessments were completed in-app at baseline and at Weeks 2, 4, and 8.

No Intervention: Wait-list Control

Participants in the wait-list control group did not receive the intervention during the initial 8 weeks. Instead, they were asked to complete the same assessments at baseline, Weeks 2, 4, and 8 via survey links delivered by text message. After Week 9, participants were granted access to the *DodaMe* app.

7. Outcome Measures

Primary Outcome:

- Stress: Perceived Stress Scale–10 items (PSS-10, Korean version)

Range: 0–40 (higher = greater stress)

Time Frame: Baseline, Weeks 2, 4, and 8

Secondary Outcomes:

- Depression: Patient Health Questionnaire–9 items (PHQ-9, Korean version)

Range: 0–27 (higher = more severe depression)

Time Frame: Baseline, Weeks 2, 4, and 8

- Anxiety: Generalized Anxiety Disorder–7 items (GAD-7, Korean version)

Range: 0–21 (higher = more severe anxiety)

Time Frame: Baseline, Weeks 2, 4, and 8

- Resilience: Brief Resilience Scale (BRS, Korean version)

Range: 1.0–5.0 (higher = greater resilience)

Time Frame: Baseline, Weeks 2, 4, and 8

8. Sample Size and Randomization

A total of 261 individuals were screened. Of these, 50 were excluded (46 scored below 14 on the PSS-10, 4 declined randomization). The final sample included participants who provided informed consent and were assigned de-identified IDs.

Participants were randomized to either the intervention group or the wait-list control group using simple randomization (<https://www.randomizer.org/>). Randomization was conducted by a research assistant not involved in data collection or outcome assessment. The principal investigator remained blinded to the allocation process to minimize bias.

An a priori power analysis (G*Power 3.1, repeated-measures ANOVA) indicated a minimum of 128 participants (64 per group) was required to detect a medium effect ($f = 0.25$) with 80% power at $\alpha = 0.05$.

9. Data Collection and Management

Data were collected via the mobile application and online surveys. All data were de-identified at export, and participants were assigned unique IDs. Only the principal investigator and a designated data manager had access to the de-identified dataset.

All study records will be securely stored for three years after study completion in compliance with institutional and national guidelines. After this retention period, electronic files will be permanently deleted, and physical records securely destroyed.

10. Statistical Analysis Plan

All analyses will follow the intention-to-treat (ITT) principle, including all randomized participants with available data. Descriptive statistics will summarize baseline demographic and clinical characteristics.

Primary Analysis

- The primary outcome is perceived stress (PSS-10).
- Changes in stress scores across time points (Baseline, Weeks 2, 4, and 8) between the intervention and wait-list control groups will be examined using generalized estimating equations (GEE) with an appropriate correlation structure to account for repeated measures.

Secondary Analyses

- Depression (PHQ-9), anxiety (GAD-7), and resilience (BRS) will be analyzed in the same manner as the primary outcome.
- Effect sizes and 95% confidence intervals will be reported for all outcomes.

Handling of Missing Data

- Missing data will be addressed using multiple imputation methods, assuming data are missing at random (MAR). Sensitivity analyses will be conducted to assess the robustness of findings.

11. Adverse Events / Safety Monitoring

Although classified as minimal risk, safety procedures were implemented. All research staff were licensed mental health professionals. Participants were provided with direct contact information for the research team to report discomfort or adverse experiences.

Participants also received information about local mental health welfare centers and suicide prevention centers, with emergency contacts provided at enrollment. If severe depression, anxiety, or stress symptoms were reported, participants were promptly referred to appropriate mental health services.

12. Ethical Considerations

The study was reviewed and approved by the Institutional Review Board of The Catholic University of Korea, Medical center(No. MC23FNSI0059). Written informed consent was obtained from all participants prior to study entry. All participants provided written informed consent. Confidentiality and the right to withdraw without consequence were guaranteed. Participants in the wait-list control arm were granted access to the intervention after the study period.

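### Intervention-arm scores are collected inside the treatment app, which ties missing outcomes to non-engagement in one arm only; the MAR imputation plan does not address this

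*Combined protocol and SAP*

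**What the plan says.** The two arms have different routes to an outcome score.

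- **Intervention arm (section 6).** "Participants assigned to the intervention group received a text message with a link to install the" DodaMe program, so installation comes after assignment. Of the scores themselves, the section says: "Assessments were completed in-app at baseline and at Weeks 2, 4, and 8". Weeks 5–8, leading up to the last assessment, consist of activities that participants choose voluntarily.
- **Control arm (section 6).** The same assessments at the same times, "via survey links delivered by text message".
- **General statements.** Section 4: "The intervention was delivered entirely via a mobile application, and outcome assessments were conducted online". Section 9: "Data were collected via the mobile application and online surveys". Both fit the two-route description, and neither rules out a survey link for intervention participants.
- **Screening.** Section 8 reports that "46 scored below 14 on the PSS-10" and were excluded, so a PSS-10 score was taken to establish eligibility. Whether it also served as the baseline score is not stated.
- **Analysis (section 10).** The ITT analysis is described as "including all randomized participants with available data". On missing data: "Missing data will be addressed using multiple imputation methods, assuming data are missing at random (MAR"; one further sentence promises sensitivity analyses for robustness, with no method, assumption or arm named.

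**The concern.** As described, an intervention participant has a score only after installing and opening the treatment. A control participant has one after answering a link. Missingness may therefore differ between arms in amount and in cause.

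Never-installers are the sharpest case. The program is delivered only through the app, so they receive none of it, and as described they have no in-app score, not even at baseline. The wording on the ITT set does not say whether they stay in. If they are dropped, or imputed from installers in their own arm, the analysis credits them with a benefit they could not have had. That runs against the ITT principle that section 10 adopts.

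For participants who install and later stop answering, MAR fails if their unseen stress differs from what their earlier scores predict. An unspecified sensitivity analysis could be met by a second MAR model, which would not show this. At stake is the between-arm PSS-10 contrast, particularly at Week 8.

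**Working it through.** **Yardstick.** Section 8 plans for f = 0.25, which for two groups is d = 2 × 0.25 = 0.5 SD. A two-group F test with one measurement, 80% power and alpha 0.05 gives N = 128 (power 0.801), which reproduces the plan's figure. It is used here only as a scale for the biases below.

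**Inputs.** From the documents: the two collection routes, MAR imputation, and 261 − 50 = 211 people left after exclusions. Assumed: all 211 randomised, split 105/106; all missing rates, gaps, correlations and installation rates. None of these is given.

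**1. Never-installers.** Let p be their share of the intervention arm and E the effect in installers, with no effect and no other difference in never-installers. The true ITT effect is (1 − p) × E. Dropping them, or imputing them by arm under MAR, returns E. The bias towards the program is p × E. With E = 0.5 SD:

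| Never-installers | True ITT effect | Estimate | Bias |
|---|---|---|---|
| 5/105 (5%) | 0.476 | 0.50 | 0.02 |
| 10/105 (10%) | 0.452 | 0.50 | 0.05 |
| 21/105 (20%) | 0.40 | 0.50 | 0.10 |

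In simulation (4,000 trials per cell, 20 imputations by arm, correlation between visits 0.5 / 0.7), coverage of the nominal 95% interval was 95.1 / 94.0%, 93.6 / 92.7% and 90.0 / 87.4% respectively. With no effect and no gap, the bias was 0.00 and two-sided rejection 4.1–4.9%.

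**2. Participants who stop answering.** Let m be the share missing at Week 8 and D the gap in SD between their true scores and the imputed ones (positive means more stressed than imputed); 1 is intervention, 0 is control. The bias towards the program is about m1 × D1 − m0 × D0.

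- 30% vs 10% missing, no gap in either arm: 0. Unequal missingness alone does no harm.
- 30% vs 10%, D1 = 0.3, D0 = 0: 0.30 × 0.3 = 0.09 SD.
- Same, D0 = +0.3: 0.09 − 0.03 = 0.06 SD. Same, D0 = −0.3: 0.09 + 0.03 = 0.12 SD.
- 30% vs 10%, D1 = −0.3, D0 = 0: 0.09 SD against the program.
- 30% in both arms, D1 = D0 = 0.3: 0.

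Under no true effect, the second case gave 8.5 / 11.9% two-sided rejection at correlation 0.5 / 0.7, against 4.0 / 4.4% with no gap.

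**3. What the remedies do.** Imputing never-installers from the control arm recovers 0.40 SD in the 20% row above. It does not remove a gap-related bias: with no effect, 20% never-installers and D = 0.3, the bias is 0.20 × 0.3 = 0.06 SD, and control-based imputation leaves 0.048 of it. Control-based imputation of all missing intervention scores leaves 0.067 / 0.062 of the 0.09 SD in section 2's second case. Shifting the imputed values by a delta equal to the true gap brings the bias to 0.00. The true gap is unknown, so delta has to be varied.

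**4. Tipping points.** With 30% of the intervention arm missing, significance is lost at delta = (estimate − 1.97 × SE) / 0.30, with SE 0.151 / 0.117.

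- Estimate 0.50 SD: 0.68 / 0.90 SD.
- Estimate 0.35 SD: 0.18 / 0.40 SD.

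**The case against.** **No differential missingness is reported.** The documents contain no report of unequal completion, of non-installation, or of the absence of a fallback route. A reader might infer that the intervention arm had no other way to answer, or that its data were in fact lost selectively. The text supports neither reading. What stands is that the only route described for that arm runs through the treatment.

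**Eligibility narrows the problem.** Section 5 requires an Android device and competence with digital devices, which removes two obvious reasons for not installing, and both arms start from a text-message link. This may keep never-installers few. It does not deal with low motivation.

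**Sensitivity analyses are already promised.** True, so it would be wrong to say the plan has none. But nothing commits them to a departure from MAR, or to treating the arms separately.

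**The larger figures need extreme inputs.** A bias of 0.20 SD takes 40% missing together with D = 0.5. Given screening and three earlier visits, the residual SD is √(1 − 4r²/(1 + 3r)), or 0.77 at r = 0.5 and 0.61 at r = 0.7, so D = 0.5 is 0.65–0.82 residual SDs. At the mild end, 10% missing and D = 0.2 give 0.02 SD. An observed effect of the planned 0.50 SD would survive any gap in the 0.2–0.5 range at 30% missing; one of 0.35 SD might not.

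**The simulation is not the planned model.** It tests one baseline-to-Week-8 contrast, not the GEE over four time points. The rejection and coverage figures do not transfer directly; the bias formulas describe the Week 8 contrast.

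**Retaining never-installers changes nothing by itself.** Correct: imputed by arm, they give the same estimate as when dropped. Retention matters because control-based imputation and delta shifts can then act on them.

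**Conclusion.** The concern holds, as a point that should be settled before analysis. Outcome collection is tied to engagement in one arm only, and MAR imputation with an open-ended analysis set and unspecified sensitivity analyses does not address it.

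If the program works for installers and never-installers have no other gap, the bias is towards the program: 0.02–0.10 SD for 5–20% never-installers and a 0.5 SD effect. This assumes that they are dropped or that imputation draws on installers in their own arm; the plan does not say which. It vanishes if the program has no effect and there is no gap.

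For participants who stop answering, a reader might infer a bias in the program's favour. The documents do not fix a direction: it depends on the missing share and the gap in each arm, and 0.09 SD at 30% vs 10% missing is an example, not an estimate. Completion by arm and visit, with the number who never installed, would show how much room for bias there is.

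**What to change.** Before analysis, amend section 10 as follows.

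1. Keep all randomised participants, including never-installers, using the screening PSS-10.
2. Impute never-installers from the control arm. Impute other missing scores by arm, using the screening PSS-10, all observed scores and any logged app use.
3. Make the promised sensitivity analysis a delta-adjusted tipping-point analysis of PSS-10. Vary delta separately by arm until the conclusion changes, and apply it to never-installers too, because control-based imputation does not remove a gap-related bias.
4. Report completion by arm and visit, the number who never installed, and whether any out-of-app route existed.

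Sections 8 and 9 report screening and data collection in the past tense, so collection has probably ended. If any assessments remain, send the same survey link to both arms regardless of app use, and note the change of route.

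The cost is programming time, an SAP wording change, and a possibly smaller or less certain effect. If collection is open, add one text message per visit for intervention participants.

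### Does an in-app baseline, apparently taken after assignment, call for an added analysis anchored on the screening PSS-10?

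*Combined protocol and SAP*

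**What the plan says.** Section 6 (Interventions) describes data collection separately for each arm. For the intervention arm: "Participants assigned to the intervention group received a text message with a link to install the" app, and then "Assessments were completed in-app at baseline and at Weeks 2, 4, and 8". The wait-list arm was asked to "complete the same assessments at baseline, Weeks 2, 4, and 8 via survey links delivered by text message", and "After Week 9, participants were granted access to the" app.

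Section 7 (Outcome Measures) gives the same schedule for PSS-10 as for the other scales, "Time Frame: Baseline, Weeks 2, 4, and 8", with no separate screening time point. Section 5 makes a PSS-10 score of at least 14 an entry condition. Section 8 reports the exclusions as "46 scored below 14 on the PSS-10, 4 declined randomization". So a PSS-10 was scored before anyone was randomized.

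Section 8 also says "Participants were randomized to either the intervention group or the wait-list control group using simple randomization", without placing that step before or after the baseline questionnaire. Section 10 (Statistical Analysis Plan) compares change in PSS-10 over the four time points by GEE, with baseline as one of them. The only sensitivity analyses it mentions stand under missing data and are not described.

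**The concern.** A baseline completed in an app that is sent only after assignment must itself come after assignment. PSS-10 is self-reported, and participants in a wait-list trial know which arm they are in. Someone who has just been given the programme, or just been told to wait, might answer differently for that reason alone. Randomization does not protect a measurement taken after allocation.

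Because the primary analysis is a comparison of change, an error confined to the baseline visit in one arm would carry into every follow-up contrast and could imitate or hide a benefit. A PSS-10 known to precede randomization exists for everyone enrolled, yet no planned analysis uses it. An additional model anchored on that score therefore looks like a cheap safeguard.

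**Working it through.** **1. What the text establishes about order.** The install link follows assignment, and the intervention arm's baseline is in-app; joined, these imply baseline after assignment. Against this, neither sentence is written as a sequence, Section 8 gives no timing, and Section 7 has no screening visit. Everyone enrolled already had a qualifying PSS-10, which could be the baseline value; the in-app wording would then be a slip. Both readings remain open. Nor is assignment the same as exposure: the documents do not say that programme content was used before the baseline questionnaire.

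**2. Inputs.** From Section 8: 261 screened and 46 + 4 = 50 excluded, so N = 261 − 50 = 211. Assumed, because the documents do not give them: equal arms, complete data, exchangeable correlation ρ of 0.5 or 0.7, and shifts s in SD units. The plan states no figure for this point that could be reproduced.

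**3. What a baseline-only shift would do to the planned analysis.** Take time as categorical with a free group difference at baseline, and no true effect. The 3-df group-by-time test has noncentrality 0.75·s²·N / [4(1 − ρ)].
- s = 0.1: 0.75 × 0.01 × 211 / 2 = 0.79 (ρ = 0.5) and 0.75 × 0.01 × 211 / 1.2 = 1.32 (ρ = 0.7). Rejection 10% and 14%.
- s = 0.2: 3.165 and 5.275. Rejection 29% and 46%.

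Here each point of shift moves each follow-up contrast by one point. Section 10 does not give the time coding, and other codings pass less. With linear time at 0, 2, 4 and 8 weeks, the mean is 3.5 and the sum of squared deviations is 12.25 + 2.25 + 0.25 + 20.25 = 35. A unit baseline shift changes the slope by 3.5/35 = 0.1 per week, or 0.8 at Week 8. With baseline as a covariate, only ρ times the shift passes (0.5 to 0.7).

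**4. What the added model could show.** It would compare Weeks 2, 4 and 8 between arms, adjusted for screening PSS-10. With equal correlations, its gap from the planned estimate equals the baseline difference adjusted for screening, with SE = √[(4/N)(1 − ρ²)] = 0.119 (ρ = 0.5) or 0.098 (ρ = 0.7).
- 95% CI half-width: 0.23 or 0.19 SD. With a screening correlation of only 0.3 it is 0.26 SD; with no adjustment, √(4/211) = 0.138 gives 0.27 SD.
- A true 0.2 SD shift gives a CI that excludes zero in 39% or 53% of trials (33% at correlation 0.3; 31% unadjusted).

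**5. What the added model would cost.** Section 6 gives the arms different collection routes at every visit. A route difference that is constant over visits cancels in the change analysis of step 3. It does not cancel in the added model, whose 3-df group test has noncentrality (s²N/4) × 3 / (1 + 2ρ − 3ρ²). At s = 0.2, s²N/4 = 0.04 × 52.75 = 2.11.
- ρ = 0.5: 2.11 × 3 / 1.25 = 5.06, rejection 45%.
- ρ = 0.7: 2.11 × 3 / 0.93 = 6.81, rejection 58%.

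The planned test stays at 5% in the same setting. A gap between the two estimates therefore cannot tell a baseline-only shift from a route effect.

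**The case for a change.** The strongest case for action is that the text needs attention on either reading. If baseline followed assignment, the starting point of the primary contrast is unprotected. If the screening score is the baseline, the in-app sentence is wrong. The arm-specific routes point towards the first reading, since a common pre-randomization baseline would hardly need two routes. A false-positive rate of 29% to 46% under a modest shift is not trivial. The added model needs no new data collection, leaves the GEE as primary, and can be dated and labelled.

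Most of the factual part stands: the implication is fair, the order is unstated, and the arithmetic reproduces. What does not stand is the step from there to a changed analysis. The shift is hypothetical in size and direction. The model applies only if baseline followed allocation and the screening scores were kept and can be linked to the study IDs, and the documents establish neither. Where it does apply, it exchanges one hypothetical bias for another, and no threshold tells the reader when a gap should qualify the conclusion.

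**Conclusion.** No change to the plan follows. The documents imply, without stating, that the intervention arm's baseline PSS-10 came after assignment, and they do not say whether the eligibility score is the baseline. That is a gap in description which the trial report can fill: when each arm completed baseline relative to randomization and to learning the allocation, and, if it came afterwards, that timing and the two routes given as a limitation. A screening-adjusted estimate may be shown as descriptive context where scores can be linked, but it should not govern the conclusion.

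The possible effect is material if a shift occurred (29% to 46% rejection at 0.2 SD, 10% to 14% at 0.1 SD), but nothing in the documents shows that one did. The proposed safeguard would detect a 0.2 SD shift in only 33% to 53% of trials and would itself reject in 45% to 58% under a constant route difference of the same size. These figures assume 211 participants in equal arms, complete data, exchangeable correlations of 0.5 to 0.7 (0.3 for the lowest detection figure) and categorical time with a free baseline difference, which Section 10 does not specify. Weighing the two hypothetical biases is a matter on which reasonable statisticians would differ, and keeping the planned GEE alone is a defensible choice.

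### Does the sample size of 128 fail to match the repeated-measures ANOVA it is attributed to?

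*Combined protocol and SAP*

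**What the plan says.** Section 8 (Sample Size and Randomization) gives one power statement. It begins "An a priori power analysis (G*Power 3.1, repeated-measures ANOVA", and its result "indicated a minimum of 128 participants (64 per group) was required to detect a medium effect", with f = 0.25, "with 80% power at $\alpha = 0.05". It does not say which effect was tested (between groups, over time, or their interaction). The number of measurements entered, the correlation among them (rho), the sphericity correction (epsilon) and the convention behind f are also absent.

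Section 10 (Primary Analysis) plans a GEE: "Changes in stress scores across time points (Baseline, Weeks 2, 4, and 8) between the intervention and wait-list control groups will be examined". The question of interest is therefore a group-by-time contrast over four visits.

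Section 8 also reports recruitment in the past tense: "A total of 261 individuals were screened. Of these, 50 were excluded". The number randomised is not stated outright; 261 - 50 = 211 is implied.

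**The concern.** A repeated-measures power calculation cannot be run without the missing inputs, and with routine choices for four visits it does not return 128. That number is also the familiar answer for two independent groups compared once at d = 0.5, which for two equal groups is the same as f = 0.25. The natural suspicion is that a single-time-point calculation was labelled as a repeated-measures one.

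If so, the trial's only power statement would describe a different test from the one planned, and the 80% would not apply to the four-visit analysis. At worst the trial could have been sized too small for its primary question without anyone being able to tell.

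**Working it through.** **Inputs.** From Section 8: f = 0.25, so f² = 0.0625; alpha 0.05; power 0.80; two equal groups. From Section 10: m = 4 visits. Rho, epsilon and the convention for f are not given, so each is varied. N is the smallest even total with noncentral-F power of at least 0.80; λ is the noncentrality parameter.

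**Reproducing 128.** Two groups measured once: λ = N f², df = 1 and N - 2. At N = 128, λ = 128 × 0.0625 = 8.0 and power is 0.8015. At N = 126, λ = 7.875 and power is 0.795. The minimum is exactly 128.

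**Four visits, overall between-group effect.** λ = N f² m / (1 + (m - 1)rho), df = 1 and N - 2.

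| rho | 0.3 | 0.5 | 0.7 | 0.9 | 0.99 |
|---|---|---|---|---|---|
| N | 62 | 82 | 100 | 120 | 128 |

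N equals 128 only from rho of about 0.985.

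**Four visits, group-by-time interaction.** df = (m - 1)epsilon and (N - 2)(m - 1)epsilon.

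- Convention using rho, λ = N f² m epsilon / (1 - rho): at epsilon 1, N = 46, 32, 24 and 16 for rho 0, 0.3, 0.5 and 0.7. The largest value for rho of 0 or more is 98 (rho 0, epsilon 1/3), so 128 cannot arise here.
- Partial-eta-squared style, λ = f² N (m - 1) epsilon: N = 60 at epsilon 1 and 128 at the lower bound, epsilon 1/3. With N - 2 in place of N in λ, the values are 62 and 130.
- λ = f² N epsilon: N = 176 at epsilon 1 and 216 at epsilon 0.75.

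**Two measurements (pre-post) interaction.** With m = 2, the second convention (using N) and the third both reduce to λ = N f² with df = 1 and N - 2. That is the single-measurement formula, so N is again exactly 128. With N - 2 in λ it is 130.

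**What this shows.** At least four routes lead to 128: one measurement, a pre-post interaction, four visits at the lower-bound epsilon, and a between-group test with rho near 1. The text does not say which was used. The pre-post route matches as exactly as the single-measurement route and, unlike it, agrees with the stated method.

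**Does the answer matter for this trial?** 211/128 = 1.65, so the implied sample is 65% above the stated minimum. With complete data at 211:

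- Single comparison at f = 0.25: power 0.95. The difference detectable with 80% power is d = 0.39.
- Between-group test over four visits: power 0.996 at rho 0.5.
- Interaction at epsilon 1: above 0.99 under the first two conventions and 0.87 under the third.
- Third convention at epsilon 0.75: power 0.79.

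**The case for a change.** The strongest case for acting is that the stated method and number do not agree under any routine four-visit setting, and this is the only power statement in the document. Because the inputs are missing, a reader cannot tell which effect the 80% refers to. Nor is 128 conservative under every convention: with λ = f² N epsilon the four-visit interaction has power of only 0.65 at 128, and at epsilon 0.75 it needs 216, slightly more than the implied 211. The remedy would cost one look at the software record and one reworded paragraph.

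The part about missing detail stands. The part about low power is weak, because every unfavourable figure comes from a single convention that the protocol does not mention; under the other two, interaction power at 128 and epsilon 1 is about 0.99 or higher.

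The obvious rewording also carries a risk. Redescribing 128 as a two-sample comparison at one time point would be false if the record shows a pre-post repeated-measures run. If the record does support that wording, the paragraph would still carry 128, f = 0.25, 80% and 0.05. Adding a detectable difference for 211 would add little, since Section 10 already commits to effect sizes with 95% confidence intervals for every outcome, and those will show the precision achieved.

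**Conclusion.** The concern identifies a real reporting gap but not an error that requires a change. The figure of 128 is not what ordinary four-visit settings give, yet it is exact for a two-measurement interaction under some conventions as well as for a single comparison. It is neither shown to be wrong nor traceable from the text. Using an ANOVA calculation as a planning approximation for a GEE is common and acceptable.

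The consequence is negligible. Recruitment is described as complete, and the implied 211 exceeds the stated minimum by 65%. Among the four-visit settings tried, 211 falls short of 80% power only under one unstated convention with epsilon below 1, and at epsilon 0.75 it does so narrowly (0.79).

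This rests on two assumptions: that all 211 people left after exclusions were randomised, and that data are complete. Loss to follow-up would lower the power, but it would not make the origin of 128 any more or less relevant. The software inputs and the number randomised are details a trial report would normally supply. Neither enrolment, the analysis nor the conclusions depend on them.
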